### 3.3.1.2.6. Mean overall scores on the EPDS

The score of each participant on the EPDS will be calculated automatically after each pre-specified assessment. We will then compute the mean overall score on the EPDS for each experimental group overall and for each month.

### 3.3.1.2.7. Mean overall score on the EMA assessments

Mood, energy, enjoyment, sleep and worry will be assessed through a visual analogue scale (VAS) over-imposed on a 5-point Likert scale. For participants allocated to the retrospective plus momentary assessment condition, we will compute the overall score on each domain for each period of each assessment day.

## 3.4. Materials and Equipment

### 3.4.1. Survey questionnaires

#### 3.4.1.1. Non-validated survey questionnaires

##### 3.4.1.1.1. Personal demographic information

We will administer a survey (Appendix 1) to collect information on a woman's age group, ethnic background, marital status, employment status, level of education, smartphone or tablet computer ownership, pregnancy history, and previous history of depression.

##### 3.4.1.1.2. EMA assessments

We will assess mood, energy, enjoyment, sleep and worry using VAS scales, over-imposed on a 5-point Likert scale (Appendix 2).

##### 3.4.1.1.3. Contextual information

Following the EMA assessments, we will administer 2 questions asking about the respondents' current location (framed in semantic terms: home, work) and her current activity (e.g., working, shopping) (Appendix 3).

##### 3.4.1.1.4. Post-study acceptance survey

Participants taking part in the *App through a BYOD approach* study, will be asked to complete a post-study survey at the end of their participation (Appendix 4).

#### 3.4.1.2. Validated survey questionnaires

##### 3.4.1.2.1. Whooley questions

The Whooley questions (Appendix 5) were developed by Whooley and colleagues (1997) as a case-finding instrument for depression in primary care. This 2-question instrument screens for depressed

mood and anhedonia that have been present during the past month. Respondents are required to answer Yes or No to each of these questions. An affirmative answer to any of them should be followed by further assessment, including the use of a validated screening instrument (such as the EPDS or the Patient Health Questionnaire 9-item) or referral to a general practitioner or a mental health practitioner. The sensitivity of the Whooley questions has been estimated at 96% and their specificity at 57% (Whooley, Avins, Miranda et al. 1997).

### 3.4.1.2.2. Edinburgh Postnatal Depression Scale (EPDS)

The EPDS (Appendix 6) is a 10-item self-administered survey questionnaire that was developed to screen for PND in the community (Cox, Holden & Sagovsky 1987). This instrument screens for clinical symptoms such as feelings of guilt, sleep disturbance, reduced energy levels, anhedonia and suicidal ideation that have been present during the 7 days preceding the administration of this survey questionnaire. Each question is scored on a 4-point scale ranging from 0 to 3 points. A final overall score is calculated by adding the scores from each question. Overall scores between 10 and 12 points suggest increased risk for depression; scores of 13 points or above indicate that the diagnostic criteria for major depression disorder have probably been met (Allbaugh, Marcus, Ford et al. 2015). In addition, those administering the EPDS should always pay attention to the answers given to item 10, as it deals with suicidal thoughts. In both instances, a clinical assessment for depression should be provided.

The EPDS is a valid and reliable tool for identifying women at risk of PND, both during pregnancy and postpartum, and is sensitive to changes in the severity of depression over time (Cox, Holden, Sagovsky 1987). The EPDS can be reproduced without further permission provided that the original source of the scale is cited in each reproduced copy.

### 3.4.2. Software

For the study using tablet computers in antenatal clinics, we will use SNAP Surveys to create the app versions of the (i) personal demographic information survey questionnaire, (ii) the Whooley questions, and (iii) the EPDS.

For the study using an app through a BYOD approach, we will use SNAP Surveys to present the (i) informed consent form [*mHealth for the EMA of mood during pregnancy – Informed Consent Form, Version 1.2, dated 19 January 2017*], (ii) the personal demographic information survey questionnaire, (iii) the Whooley questions, and (iv) the EPDS. In addition, we will use a bespoke app developed by [name] to collect (i) the EPDS, (ii) EMA assessments, (iii) the Contextual Information survey, and (iv) the post-study survey. This app will also include additional features providing additional information about mood during pregnancy and a list of available resources.

### 3.4.3. Mobile devices

For the assessment of tablet computers in antenatal clinics, we will use iPads to deliver the survey questionnaires. For the assessment of an app using a BYOD approach, we will use any tablet computer to collect the baseline assessments, and any Android or iOS handset to install the bespoke app.

## 3.5. Data collection

### 3.5.1. Pilot phase & Co-design sessions

#### 3.5.1.1. *Tablet computers in antenatal clinics*

We will conduct a heuristic evaluation of the user interface of the two layouts (i.e., scrolling versus paging) of the survey questionnaires in order to identify any usability issues prior administration in general practices or midwifery services. During this process, a member of the research team will

evaluate the user interface of the survey questionnaires against the 10 usability principles proposed by Jakob Nielsen (Nielsen 1995).

In addition, we will pilot the administration of both layouts (i.e., scrolling versus paging) of the survey questionnaires with female staff members at the Department of Primary Care and Public Health, Imperial College London (ICL). If possible, we will involve members of the public or members of relevant patient groups in the pilot phase. We expect that this would allow us to identify any usability issues or problems with the study design.

Lastly, during the pilot phase we will develop a script of the instructions that will be given to participants during the study, as well as our standard operating procedures (SOP).

### **3.5.1.2. *App through a BYOD approach***

As part of a patient and public involvement and a service development initiative, we will conduct workshops with potential end users of the bespoke app and with interested stakeholders (including general practitioners, nurses, midwives, consultants, health visitors, carers, and members of charity or advocacy groups) to gather feedback on the initial prototype of the app. This feedback will be incorporated into the final working version of the bespoke app.

## **3.5.2. Study Phase**

### **3.5.2.1. *Tablet computers in antenatal clinics***

After obtaining written informed consent from our participants, a member of the research team will impart verbal instructions on how to complete the survey questionnaires. Participants will be informed that their results on the EPDS will be communicated to her clinician and that they will be available for discussion during her antenatal appointment.

Moreover, the member of the research team imparting the instructions will explain to participants that they can ask for help at any point while completing the survey questionnaires, and that all questions should be directed to a member of the research team. We will offer help with the use of the devices. However, we will not offer help reading questions out loud to participants, as this corresponds to an interview-administered survey questionnaire in which different factors could influence the quality of the survey responses.

Participants will be asked to complete all the survey questionnaires while waiting for their appointment in the waiting area of participating general practices, midwifery services or hospitals.

### **3.5.2.1.1. *App Screening – Scrolling layout***

Participants allocated to this intervention arm will receive an iPad running the survey questionnaires (personal demographic information, Whooley questions, and EPDS). We will consider that a participant has started completing the survey questionnaires as soon as they press the button *Start* displayed on the screen. Immediately after, a screen will be displayed which will contain an outline of the survey questionnaires to be completed and basic instructions on how to complete them. In this experimental group each survey questionnaire will be presented on a single screen. Therefore, participants will need to scroll vertically in order to answer all the questions. They will be able to scroll up and down as they wish and to modify the answers to previous question as long as they do it before submitting their answers. However, once they have submitted their responses, a message acknowledging their participation will be displayed on the screen of the iPad Air and they will no longer be able to modify their answers. Validation procedures will ensure that participants will not be able to submit a survey with unanswered questions. Once the surveys have been completed, the participants will return the tablet to a member of the research team. Subsequently, the participant will be given printed material

containing additional information on maternal mental health, and a printed letter [*Antenatal mental health screening – Communicating results to the clinician*, version 1.0, dated 28 April 2015] with her score on the EPDS will be given to her clinician.

### 3.5.2.1.2. App Screening – Paging layout

Participants allocated to this intervention arm will receive an iPad Air running the survey questionnaires (personal demographic information, Whooley questions, and the EPDS). We will consider that a participant has started completing the survey questionnaires as soon as they press the button *Start* displayed on the screen. Immediately after, a screen will be displayed which will contain an outline of the survey questionnaires to be completed and some basic instructions on how to complete them. In this experimental group each survey questionnaire will be presented using a paging layout. Therefore, participants will only see one question on the screen at any given time. They will need to select and submit their answer to the current question before being able to move on to the next question. Participants will not be allowed to re-visit already answered questions. Validation procedures will ensure that participants will not be able to submit an unanswered question. Once the surveys have been completed, the participants will return the tablet to a member of the research team. Subsequently, the participant will be given printed material containing additional information on maternal mental health, and a printed letter [*Antenatal mental health screening – Communicating results to the clinician*, version 1.0, dated 28 April 2015] with her score on the EPDS will be given to her clinician.

### 3.5.2.1.3. Communicating answers to the Whooley questions and EPDS scores to clinicians

For participants in both experimental groups (i.e., *App Screening – Scrolling*, and *App Screening – Paging*) a member of the research team will complete the *Antenatal mental health screening – Communicating results to the clinician* (Version 1.0, dated 28 April 2015) form immediately after a participant has completed the study. In this letter, the researcher will write down the participant's answers to the Whooley questions and her score on the EPDS; a legend in this letter will aid with the interpretation of scores. In addition, the researcher will be able to tick a box that indicates that the participant is experiencing suicidal thoughts (as assessed by question 10 of the EPDS). This letter will be handed over to the clinician before the antenatal consultation for that participant takes place.

### 3.5.2.1.4. Duty of care

All participants will receive a sheet of paper containing additional information about mental health during pregnancy and a list of useful resources (i.e., links to the information leaflets produced by the Royal College of Psychiatrists (RCP).

In addition, we will agree a protocol with the clinicians in our participating general practices, midwifery services or secondary care sites to ensure that those participants who receive a score suggestive of depression are assessed and managed as recommended by the *Antenatal and postnatal mental health: clinical management and service guidance* NICE guideline (NICE 2014) and their local pathways.

### 3.5.2.2. App through a BYOD approach

After obtaining written informed consent from our participants, a member of the research team, a member of the clinical care team, or a CSO will ask the participant to complete a personal demographic survey, the Whooley Questions and the EPDS using a tablet provided by the research team. At this point, participants will be randomised to one of two experimental conditions: *retrospective assessment*, or *retrospective plus momentary assessment*. After random allocation has taken place, participants will be given a Quick Response (QR) code to scan with their own smartphone, or otherwise directed to download and install the app. This app will be free of charge and it will **not** offer any in-app purchases. After installing this app, participants will need a code in order to activate their account and

be able to take part in the study. This activation code will be generated in advance by the study coordinator. We will communicate a participant's baseline EPDS score to her clinician (i.e., midwife or consultant) if it is 10 points or higher, or if she has been identified as having increased risk of self-harm as measured by question 10 of the EPDS. We will do this through the document *Antenatal mental health screening – Communicating results to the clinician (Version 1.0, dated 28 April 2015)*. Participants will be required to take part for 6 months.

### 3.5.2.2.1. Retrospective assessment

Participants in this condition will be asked to complete the EPDS once a month for 6 months. The day on which participants are required to complete the EPDS will be selected at random from each calendar month, and with no less than 2 weeks in between 2 consecutive sampling periods. On that day, we will select a random time between 10.00 and 22.00 to administer the EPDS. At that time, a notification will be displayed on a participant's phone asking her to complete the EPDS. They will then be able to accept the request or reject it. Outside the sampling period, participants will be allowed to complete as many assessments as they wish to. However, during the sampling period, participants will not be allowed to complete any additional assessments.

### 3.5.2.2.2. Retrospective plus momentary assessment

Participants in this condition will be required to complete a sampling period of 4 consecutive days once a month for 6 months; this period will be randomly selected from each calendar month, with no less than 2 weeks in between 2 consecutive sampling periods. The sampling period will start on day 1 with an administration of the EPDS and will conclude with another administration of the EPDS on day 4. In between (i.e., days 1 to 4 of the sampling period) participants will be asked to complete EMA assessments on mood, sleep, energy, enjoyment and worry plus 2 contextual information questions 3 times a day. The sampling hours will run between 10.00 and 22.00. This 12-hour window will be divided into 3 periods of 4 hours each, and with no less than one hour in between 2 consecutive assessments. Participants will receive a notification prompting them to complete the assessment at random times within each 4-hour period. Participants will have the option to accept or reject the request in the notification. Outside the sampling period, participants will be allowed to complete as many assessments as they wish to. During the sampling period however, participants will not be allowed to complete any additional assessments.

### 3.5.2.2.3. Duty of care

The EPDS is a screening tool that indicates the likely risk of depression during pregnancy or postpartum. Scores between 10 and 12 points indicate an increased risk of depression; whereas a score of 13 points or more indicates that the diagnostic criteria for major depression have probably been met. In both cases, further assessment is warranted to confirm a diagnosis of depression. In addition, question 10 of the EPDS deals with a woman's risk of self harm. Scores of between 1 and 3 points on this question warrant further assessment.

For every participant, we will collect at baseline the following contact details:

- GP: telephone number, email address and postal address
- Designated clinician: telephone number, email address and postal address

The system will send an email notification to the study coordinator if any participant:

- Scores 10 points or more on the EPDS
- Scores 1 point or more on Question 10 of the EPDS regardless of her overall score on the EPDS
- Completes more than 2 instances of the EPDS in one day

Upon receiving any notification, the study coordinator will notify the participant's risk to all of her contacts via the telephone. This will be followed up by a written notification using the documents *Antenatal mental health screening – Letter to the GP (Version 1.1, dated 06 December 2015)* or *Antenatal mental health screening – Communicating results to the clinician (Version 1.0, dated 28 April 2015)* being posted to the participant's GP and her designated clinician. The study coordinator will action this within 24 hours.

#### 3.5.2.2.4. Feedback by a human supporter

Sites choosing to take part in this part of the study, will identify a member of the clinical care team who will be in charge of reviewing participants' data, and of providing feedback to them through a desktop web interface that will be developed by [name] (they will not be using an app on their personal devices for this purpose). The type of feedback that participants will receive will be through templates that the designated member of staff will tailor to each participant. The most appropriate content for these templates will be identified through the co-design sessions outlined in *Section 3.5.1.2*. The designated member of the clinical care team **will not** replace the person conducting the procedures outlined in *Section 3.5.2.2.2. Duty of care*. In addition, the provision of feedback to participants **is not** intended to be an emergency or out-of-hours service. No personal contact details will be exchanged between participants and the designated member of the clinical team.

The designated members of the clinical team will be required to spend no more than 30 minutes once a week reviewing participants' data and providing feedback. After the study, they will be asked to take part in semi-structured interviews to assess their general sense of usefulness of this method and to complete a post-study survey (Appendix 7).

For participants in this experimental condition, we will assess their sense of connectedness and general sense of usefulness through additional questions in the post-study acceptance survey (Appendix 4).

#### 3.6. Sample size

According to Matthey (2004), the minimal clinically significant difference for the EPDS (calculated using a reliable change index (RCI) and a standard deviation of 4) is 4 points. Therefore, for the study using tablet computers in antenatal clinics, in order to demonstrate a one-sided equivalence between the two layouts (i.e., scrolling versus paging) of the EPDS using an additive model (i.e., the mean score difference between the two groups not exceeding 3 points) with an alpha level of 0.025, power of 0.80 and a standard deviation of 4 we would need 126 participants. In addition, in order to demonstrate the PPV, PNV and FOR of the Whooley questions we would need at least 30 events (i.e., women scoring 10 points or higher on the EPDS). Assuming a prevalence of depression in pregnant women of 12%, we would need to recruit 250 participants. For these reason, we will aim to recruit a total sample of at least 300 participants.

For the app through a BYOD approach study, we aim to determine adherence to sampling protocols. We have chosen to relate the proposed sample size to the 95% confidence interval for the rate, as recommended by the Research Design Service in London. Therefore, we would need 96 participants in each arm with a 95% confidence level and a confidence interval of 10. This translates into a total sample of 192 (i.e., 96 participants in each experimental group). For this reason, we will aim to recruit at least 200 participants.

For the additional condition where participants will receive feedback from a designated member of the clinical care team, we aim to recruit 30 participants.

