### 3.8.2. Inferential statistics

#### 3.8.2.1. Positive predictive value (PPV)

We will calculate the PPV of the Whooley questions by dividing the total number of pregnant women who answered *Yes* to any of the Whooley questions and scored 10 points or higher on the EPDS by the total number of women who answered *Yes* to any of the Whooley questions. We will present this value in percentage form.

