#### 3.8.2.2. Negative predictive value (NPV)

We will calculate the NPV of the Whooley questions by dividing the total number of pregnant women who answered *No* to both Whooley questions and scored 9 points or lower on the EPDS by the total number of women who answered *No* to both Whooley questions. We will present this value in percentage form.

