#### 3.8.2.3. False omission rate (FOR)

We will calculate the FOR of the Whooley questions by dividing the total number of pregnant women who answered *No* to both Whooley questions and scored 10 points or higher on the EPDS by the total

number of women who answered *No* to both Whooley questions. We will present this value in percentage form.

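### The 30-event rule in section 3.6 does not set the precision of PPV, NPV or FOR, and all three are to be reported without intervals

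*Combined protocol and SAP*

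**What the plan says.** For the tablet study, section 3.6 gives a sample-size reason specific to the Whooley accuracy measures: "in order to demonstrate the PPV, PNV and FOR of the Whooley questions we would need at least 30 events". The events are defined there as "women scoring 10 points or higher on the EPDS". The conversion follows: "Assuming a prevalence of depression in pregnant women of 12%, we would need to recruit 250 participants". Together with the layout comparison this leads to the target: "we will aim to recruit a total sample of at least 300 participants". Section 3.6 gives no expected value, confidence level or interval width for any of the three measures.

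The analysis sections define the measures on other groups. Section 3.8.2.1 divides PPV by the "total number of women who answered *Yes* to any of the Whooley questions". Section 3.8.2.2 takes the number of women who answered No to both questions and "scored 9 points or lower on the EPDS by the total number of women who answered *No* to both Whooley questions". Section 3.8.2.3 uses that same Whooley-negative denominator for FOR, with EPDS 10 or more in the numerator. Each of the three sections ends with the same instruction: "We will present this value in percentage form". None names a confidence interval.

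Section 3.4.1.2.1 cites 96% sensitivity and 57% specificity for the Whooley questions as literature values. Neither is a study objective, endpoint or planned analysis.

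**The concern.** A sample-size statement should tie the number recruited to the precision of what will be reported. Here the target fixes the expected number of EPDS-positive women. That number is the denominator of sensitivity, which the plan does not report. The reported proportions have Whooley-positive or Whooley-negative women as denominators, and section 3.6 calculates neither count.

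The practical risk lies with FOR and its complement NPV. If few EPDS-positive women answer No to both questions, FOR depends on a handful of women. Printed as a lone percentage, 0% or 0.7% could be read as showing that the Whooley questions miss almost nobody, with nothing on the page to show how much higher the rate could be. Section 6.5 says the findings will inform a later clinical trial of mobile-based screening, so the figure is likely to be reused.

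**Working it through.** **Inputs.** Event target 30, prevalence 12% and N = 300 (section 3.6). Sensitivity 96% and specificity 57% (section 3.4.1.2.1), assumed here to hold against EPDS 10 or more. Prevalence range 7.4% to 20% (section 1). Sensitivity of 80% and specificity of 90% are my own assumptions, used only to show a range.

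**The plan's figure.** Participants = events / prevalence = 30 / 0.12 = 250. This reproduces exactly.

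**What the count enters.** Let TP, FP, FN and TN be the cells of the Whooley by EPDS table.

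- Events = TP + FN
- PPV = TP / (TP + FP)
- NPV = TN / (TN + FN)
- FOR = FN / (TN + FN) = 1 − NPV
- Sensitivity = TP / (TP + FN)

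Only sensitivity has the event count as its denominator.

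**Expected table at N = 300.**

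- Events: 300 × 0.12 = 36; non-events: 264
- TP = 0.96 × 36 = 34.6; FN = 0.04 × 36 = 1.44
- TN = 0.57 × 264 = 150.5; FP = 0.43 × 264 = 113.5
- Whooley-positive: 148.1; Whooley-negative: 151.9
- Expected PPV = 34.6 / 148.1 = 23%; expected FOR = 1.44 / 151.9 = 0.95%

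**Exact (Clopper-Pearson) 95% CIs on rounded counts.**

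| Measure | Count | Estimate | 95% CI |
|---|---|---|---|
| PPV | 35/148 | 23.6% | 17.1 to 31.3% |
| FOR, none missed | 0/152 | 0% | 0 to 2.4% |
| FOR, one missed | 1/152 | 0.7% | 0.02 to 3.6% |
| FOR, two missed | 2/152 | 1.3% | 0.16 to 4.7% |

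The upper limit for 0/152 is 1 − 0.025^(1/152) = 2.4%. NPV is the complement: 151/152 = 99.3%, CI 96.4 to 99.98%.

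**Chance that no case is missed.** With 36 events, 0.96^36 = 0.230. With the number of events also random, (1 − 0.12 × 0.04)^300 = 0.236. The plan would then print FOR 0% and NPV 100%.

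**Same 36 events, different precision.**

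- At 80% sensitivity, FN = 0.20 × 36 = 7.2 among 157.7 Whooley-negatives. On rounded counts 7/158 = 4.4%, CI 1.8 to 8.9%. That interval is 7.1 points wide, against 3.6 points for 1/152.
- At 96% sensitivity and 90% specificity, Whooley-positives fall to 34.6 + 26.4 = 61.0, and the PPV interval is 44.1 to 70.0%. Its half-width is about 13 points, against about 7 for 35/148.

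The event count is 36 throughout, so it cannot be what determines these widths.

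**Prevalence range at 96% sensitivity, N = 300.** Expected missed cases = 300 × prevalence × 0.04: 0.9 at 7.4%, 1.4 at 12%, 1.5 at 12.8% and 2.4 at 20%.

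**The case against.** The strongest reply has four parts.

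First, the events are not irrelevant. They supply the PPV numerator (about 35 of 36) and the whole FOR numerator, and recruiting 300 women in effect fixes the denominators too. This stands: the rule is connected to the measures, but it does not state or set their precision.

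Second, the precision at 300 is usable. PPV is known to about ±7 points, and FOR has an upper limit of a few percentage points when nought to two cases are missed. This also stands. A reader might infer that the study is too small, or that about 30 missed cases are needed, which at these inputs would take 30 / (0.12 × 0.04) = 6,250 women. The documents set no such requirement, and nothing here calls for a larger sample.

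Third, the 96% is a literature value for a primary-care case-finding instrument. It was not estimated against EPDS 10 or more in pregnancy, and the two instruments cover different periods (past month in Appendix 5, past 7 days in Appendix 6). A reader might infer that FOR is certain to rest on one or two women. The documents do not support that: the count depends on the sensitivity seen here, and is about 7 at 80%.

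Fourth, these are secondary objectives (2.1.2) of a feasibility study with no hypotheses about them (2.1.3), and the descriptive results in 3.8.1 would let a careful reader rebuild the 2×2 table. That limits the harm. It does not justify leaving the intervals to the reader, particularly as section 3.6 sizes the BYOD study on the 95% confidence interval of a rate. Reporting both NPV and FOR is redundant rather than wrong.

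**Conclusion.** The point holds as a mismatch between the sizing rationale and the measures, together with a reporting gap. It is not an arithmetic error and not a shortage of participants. Thirty EPDS-positive women give no basis for saying that PPV, NPV and FOR will be demonstrated, and two of those three are one quantity and its complement.

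The consequence is largest for FOR. On the plan's own inputs, the chance of a bare 0% is close to one in four, and a reported 0.7% would be compatible with a rate more than five times as high (3.6 / 0.66 = 5.5), although that is still only a few percentage points in absolute terms. These sizes assume that 12%, 96% and 57% carry over to this population and this reference standard. The mismatch of denominators and the absence of planned intervals do not depend on that assumption. The point should be corrected, but it does not threaten the study.

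**What to change.** 1. **Section 3.6.** Keep the target of 300. Replace the claim that 30 events demonstrate the three measures with the expected Whooley-positive and Whooley-negative counts (about 148 and 152 under the cited inputs) and the 95% CI widths these give for PPV and for NPV/FOR. Name the assumed prevalence, sensitivity and specificity, and show at least one lower sensitivity.
2. **Sections 3.8.2.1 to 3.8.2.3.** Report each measure with its numerator, denominator and an exact or Wilson 95% CI. State that FOR is 1 − NPV, so that the two are not read as separate evidence.
3. **Optional.** Report sensitivity and specificity against EPDS 10 or more, with CIs, from the same 2×2 table. The event count is the denominator for sensitivity: for example, 35/36 = 97.2%, CI 85.5 to 99.9%. The plan sets no precision target for it, so this is an addition and not a repair.

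The cost is a few sentences in 3.6 and 3.8 and a few lines of analysis code. No extra participants or data are needed.
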